	[name]				
	Edinburgh				
	[name]				
	[name]				
	[name]				
Study Co-ordinator	[name], Senior Researcher				
	ScotCen Social Research				
	[name],				
	[name]				
	Edinburgh				
	[name]				
	[name]				
	[contact]				
Sponsor	[name], Chief Executive Officer				
	NatCen Social Research				
	[name]				
	[name]				
	[name]				
	[contact]				
Joint-sponsor(s)/co-sponsor(s)	n/a				
Funder(s)	National Institute for Health and Care Research (NIHR)				
	NIHR Evaluation, Trials and Studies Coordinating Centre (NETSCC)				
	University of Southampton [name],				
	[name]				
	[name]				
	[contact]				

STUDY SUMMARY

Study Title	Impact of a Distress Brief Intervention (DBI) on Suicidal Ideation, Suicide Attempts and Self-harm in the immediate, short and longer term.
Internal ref. no. (or short title)	DBI Impact Evaluation on Suicide and Self-harm (DIMES)
Study Design	Mixed method evaluation
Study Participants	Adults (aged 16 and over) who access DBI, DBI Staff, individuals who have used NHS24 Mental Health Hub and GPs.
Planned Size of Sample (if applicable)	Adults who access DBI survey: 2,700 (some attrition is expected as data collection progresses) Adults who access DBI Qualitative interviews: maximum 75 (some attrition is expected as data collection progresses) Administrative dataset comparator group quantitative analysis: 2500 NHS 24 Mental Health Hub service user qualitative interviews: 15 Stakeholder focus groups: 42 – 56 (6-8 per focus group) GP survey: 20
Follow up duration (if applicable)	1 year
Planned Study Period	36 Months from start May 2022 to end April 2025
Research Question/Aim(s)	To understand whether and how DBI can reduce suicidal ideation, suicidal behaviour and self-harm among those presenting to front-line services in distress.

FUNDING AND SUPPORT IN KIND

FUNDER(S) (Names and contact details of ALL organisations providing funding and/or support in kind for this study)	FINANCIAL AND NON FINANCIALSUPPORT GIVEN
National Institute for Health and Care Research	£996,035.12
NHS service support costs	£16,380

STUDY CO-APPLICANTS

[name] [name], Chair in Health Psychology, Institute of Health and Wellbeing, University of Glasgow

[name], Lecturer In Mental Health, Institute of Health and Wellbeing, University of Glasgow

1 BACKGROUND

Suicide presents a significant challenge across the UK. In 2018₁ there were 784 deaths by suicide in Scotland. Scotland has consistently had the highest recorded UK suicide rate since the 1990's. Nearly 1 in 2 people (44.2%) who died by suicide were in contact with at least one unscheduled care service in the year before death. They were more likely to have had this contact than the general public₂ who did not die by suicide. Nearly three-quarters (73%) had contact with at least one health service in the year prior to death. In Scotland, suicide attempts are most prevalent amongst young (16-24) and middle-aged adults, although men and women in middle-age are most likely to die by suicide₃; almost half are aged 35-544. Younger adults are most likely to self-harm and experience isolation₅. Self-harm and suicidal ideation are strongly associated with a lifetime risk of suicide₆. A common driver for all the above is mental distress. Against a background of deteriorating mental health among young people pre-Covid-19, recent evidence suggests that mental distress has increased in the UK population under Covid-19, particularly amongst young adults, women, those employed pre-pandemic and those living with children_{7,8}.

Distress Brief Interventions Programme

To address the need to improve the response to adults (aged 18+) in distress highlighted by the Scottish Government (SG) Suicide Prevention₉ and Mental Health strategies₁₀, the Scottish Government (SG) developed the Distress Brief Intervention (DBI). The DBI was developed and delivered by the University of Glasgow (led by co-applicants RO and JMel) from a literature review₁₁, and consultations with service users and stakeholders. Distress is defined by DBI as '*An emotional pain for which the person sought, or was referred for, help and which does not require (further) emergency service response*'. The DBI pilot programme was launched in 2017.

The DBI programme is a unique approach to supporting those in distress who present to frontline services. It brings SG together with a DBI Central team, local NHS and voluntary DBI provider partnerships, national agencies (Primary Care, Police Scotland, Scottish Ambulance Service, Emergency Departments and NHS24), 3rd sector mental health organisations and University of Glasgow. Six delivery teams operate in four regions: one in each of Aberdeen, Borders, Inverness and three in Lanarkshire. In May 2019, DBI extended to include those aged 16-17. In June 2020, as a response to COVID-19, DBI was extended via NHS24 to gain national coverage. DBI comprises two levels. Level1 (L1) involves trained front-line staff (Primary Care, Police Scotland, Scottish Ambulance Service, Emergency Departments, Social Work and NHS24) offering a compassionate response to individuals in distress and enables referral to a Level2 (L2) service. At L2, individuals are contacted within 24 hrs and offered up to 14 days of community-based, person-centred support from trained staff. DBI explores the nature and cause of individual's distress and how they can manage it in the future. DBI service users co-create a Distress Management Plan (DMaP) with their L2 worker; the previous evaluation suggests many individuals were using their DMaP three months on from DBI intervention. Individuals are then sign-posted to and/or receive support to engage with appropriate follow-up support.

Intervention target length is currently set to two weeks (14 consecutive days) to ensure the service is brief but intervention length is tailored to individual needs. Most people (55%)

complete DBI L2 by 14 days, 25% by 21 days and 20% within a month or more. So far DBI has supported over 10,000 people. Over half (53%) of all individuals referred to DBI between November 2018 and January 2021, were assigned to at least one of the following presenting problem categories: suicidal thoughts (33%), self-harm (12%); thoughts of self-harm (8%); suicidal behaviour (6%); overdose (intentional) (10%). The deprivation profile of DBI service users (as indicated by SIMD) is skewed towards people living in more deprived areas with over half living in the two most deprived quintile areas and a fifth in the two least deprived quintile areas.

Pilot evaluation

A pilot evaluation (2018-2021₁₂) of DBI was led by co-applicants ED, JM. The evaluation consisted of a mixed-methods realist evaluation of DBI with adults (>=18 years) in four case study (Health Board) sites in Scotland. Qualitative data (n= 57 interviews/focus groups with staff who delivered DBI, and n= 20 interviews with people who received DBI) and quantitative outcome data collected and analysed. Key study findings demonstrated that the intervention was highly feasible and acceptable to practitioners and people who received the service. Pre-post measurements of distress (CORE-OM 5₁₃) demonstrated that most participants' levels of distress reduced following DBI intervention. While DBI did not specifically measure suicidal ideation, suicidal behaviour, or self-harm behaviour, qualitative feedback indicated that without DBI, approximately 10% of study participants felt they would have gone on to complete suicide. Therefore, DBI appears to be filling a critical support gap between unscheduled care, emergency service response and suicide attempts and may help to prevent or break the escalation of crisis to and unhealthy cycles of suicidal behaviour. See Logic Model in supporting documentation.

Existing evidence

A review was conducted using the following databases (2010-March 2021): Cochrane, CINAHL, PsycINFO, Web of Science Core Collection, Pubmed and Embase. Keyword searches including the terms psychosocial, intervention or strategy or best practice, suicide attempt and suicide, self-harm or self-injury or deliberate self-harm or self-mutilation or self-injurious were employed. Articles were refined by language (English). The study selection process involved screening titles in the first instance, followed by reading the abstracts. Thirty-six articles were included.

Systematic reviews have investigated the effectiveness of psychosocial interventions to reduce suicidal behaviour and risk or self-harm. These reviews found psychoanalytic and psychodynamic therapies to be effective in reducing the number of patients attempting suicide and hospital admissions14. Psychosocial and behavioural interventions that directly address suicidal ideation and behaviour were found to be effective immediately posttreatment and long term 15. Brief suicide prevention interventions were associated with reduced subsequent suicide attempts and increased follow-up care engagement₁₆. Some systematic reviews suggest psychosocial interventions provided in in- and out-patient settings may be effective in reducing future repetition of self-harm following an index episode14,17,18. The most comprehensive of these found CBT and problem-solving therapy led to fewer participants repeating self-harm at 6 and 12 months and beneficial effects for secondary outcomes of depression, hopelessness, suicidal ideation and problem solving₁₈. Other therapeutic approaches led to less frequent, but no overall reduction in the proportion of individuals engaging in self-harm at 6 or 12 months. Individual case-management and remote contact interventions (e.g., postcards, GP letters, telephone calls) were not associated with a reduction in repetition of self-harm. None of these reviews systematically assessed the role of intervention duration, intensity, setting or practitioner14,17,18. A recent narrative evidence synthesis concerning the effectiveness of approaches used in national suicide prevention programs included a meta-analysis of 12 eligible studies on brief contact intervention (BCI) from a systematic review₁₉. The study found weakly supportive evidence of the effectiveness of BCI on repeated self-harm, suicide attempt, and suicide, highlighting

methodological limitations of current evidence and concluded that further suicide prevention evaluation studies are needed. A review of international distress brief intervention research literature was undertaken to inform the development of Scotland's DBI programme₁₂. It found that despite the existence of international data exploring the effectiveness of DBI and BCI in reducing suicidal ideation, suicidal attempts and self-harm, intervention studies are small in number and scale and vary widely in format, intervention design, target population and outcome measure.

The review of existing evidence confirms that little is known about the impact of brief interventions on suicidal ideation. However, DBI programme evaluation findings suggest that DBI L2 intervention could be preventing suicidal behaviour₁₂ and further research is recommended. This study will make a significant contribution to filling this knowledge gap. The findings would support the improvement of the current DBI intervention and its wider roll-out to the UK and beyond and inform future development of integrated mental health care and suicide prevention policy and practice.

2 RATIONALE

This study aims to understand whether and how DBI can reduce suicidal ideation, suicidal behaviour and self-harm among those presenting to front line services in distress and crisis.

Suicide prevention has been a policy priority across the UK since the 1990's with some progress made but a clear recognition in recently renewed national policies⁹ that suicide prevention action must be improved. Evidence suggests that the impact of the COVID-19 pandemic is likely to be felt widely at both societal and individual levels, impacting on mental health²⁰ with self-harm and suicide rates expected to increase as the longer-term effects are felt as reflected in recent policy responses focussed on recovery²¹. The review of evidence above and recent NIHR call 18/138 Suicide Prevention in High Risk Groups highlight the scarcity of evidence and need for further research on which statutory and /or voluntary sector interventions are effective in reducing suicide, suicide attempts and self-harm. The Distress Brief Intervention is a significant new approach aimed at reducing distress and self-harm and suicidality embedded in Scotland's suicide prevention⁹ and mental health¹⁰ policy plans that has relevance across the UK and beyond. The DBI programme staff are deeply committed to building this study's learning into their continuous improvement programme.

3 THEORETICAL FRAMEWORK

The conceptual framework for this study is grounded within the Integrated Motivational- Volitional (IMV) Model of Suicidal Behaviour₂₂. The IMV model is based on the premise that factors associated with the emergence of suicidal thoughts (early life adversity/disadvantage leading to feelings of defeat and entrapment) are distinct from those that influence the transition from ideation to behaviour and understanding the process of ideation to action is crucial to preventing suicide. In the IMV, volitional moderators (e.g. access to means, planning, impulsivity, past suicidal behaviour) govern the transition from suicidal ideation to behaviour. The model proposes that suicidal behaviour is not linear but a dynamic process that for many is cyclical in nature moving from suicidal thinking to attempt and back to thoughts repeatedly over time and that over time the time between thoughts and action becomes less, lessening in turn opportunity to intervene. The IMV model incorporates evidence that those who have a history of suicidal behaviour or self-harm have higher levels of motivational factors. The IMV model is part of the training for staff who deliver the DBI intervention.

With over half of those referred to DBI presenting with self-harm, suicidal thoughts or behaviour, emerging evidence suggests that DBI has potential to fill a critical support gap for such people between unscheduled care and a crisis escalating into self-harm, suicidal ideation or behaviour. A key (not yet published) finding from the first evaluation of DBI is that 10% of those accessing DBI reported

that they would have gone on to attempt suicide or continued with their suicidal ideation if DBI had not been available to them. This suggests that DBI may be helping to prevent or break the cycle between a crisis escalating and suicidal / self-harm thoughts and behaviour.

Although the DBI intervention is focused on alleviating the distress associated with a current crisis, as it aims to equip people to better cope with future crisis it has considerable potential to prevent suicidal behaviour in in the short, medium and longer term. Understanding how the DBI intervention has helped people to break the cycle of suicidal thoughts to action or not will provide important insights into how the intervention can be further developed and optimised as a suicide prevention intervention for those with a history of self-harm, suicidal thoughts or behaviour.

4 RESEARCH QUESTION/AIM(S)

This study aims to understand whether and how DBI can reduce suicidal ideation, suicidal behaviour and self-harm among those presenting to front line services in distress and crisis.

The research questions are:

- Does DBI help people who present in crisis and distress with current or previous suicidal ideation, suicide attempts, self-harm achieve better outcomes in the immediate, short and longer term?
- How do these outcomes differ for those with different contributory and protective factors (e.g. financial, relationships, addiction, gambling), in different age groups particularly 16-24 year olds and 35-54 year olds), and by gender?
- Are there differences in experience and outcomes for people who present to DBI with suicidal ideation, suicidal behaviour or self-harm compared to other DBI service users?
- What aspects of the DBI intervention contribute to these different outcomes, how and why? (e.g. 24hr response, intensity, problem solving strategies including the distress management plan (DMaP), referral/sign-posting).
- How does the length of the DBI L2 intervention impact on the above outcomes?
- Does DBI need a Level 3 to follow-up people with suicidal ideation/ suicidal behaviour/self-harm over a longer period? If so, how should this be implemented?
- In what ways might DBI improve its contribution to positive outcomes for people who present with suicidal ideation/ suicidal behaviour/self-harm and how does this apply to other services?
- Is DBI L2 associated with a greater reduction in unscheduled health care use in the year after intervention compared to a comparator group of those who accessed NHS24 for mental health reasons prior to the introduction of DBI?
- What is the health care, social care and third sector resource use for DBI service users over the 12-month period following their DBI L2 intervention?
- What care pathways do GPs use to support people in distress with suicidal ideation, suicidal behaviour and self-harm and what is the resource use associated with this?

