5.2 Data Collection

5.2.1 Quantitative surveys for individuals accessing DBI:

Individuals accessing DBI who provide informed consent will be invited to complete a L2 DBI service users survey at their first and final DBI L2 sessions for baseline and immediate outcome data (approximately two weeks apart). These surveys will be administered by DBI L2 staff as described in section 7.1. The surveys are largely quantitative and include a combination of validated scales and bespoke closed questions as well as a small number of open questions to measure the following:

- Impact of assurance of contact 24 hours from referral.
- Level of distress₂₇, suicidal ideation, suicidal behaviour and self-harm₂₈, identifying first time/repeat disclosure
- Feelings of entrapment/hopelessness/despair₂₉
- Resilience 30
- Self-stigma₃₁
- Health related quality of life 32
- Perceptions of the DBI aspects, if any, that are most beneficial for above outcomes
- Impact of other different sources of support or life circumstances on the above outcomes
- Health, social care and third sector resource use
- Smart phone and/or email and/or postal address to enable ScotCen research team to administer the 3 month follow-up and 1 year follow-up surveys electronically or address for postal.

Equality and diversity questions are not included in the surveys because demographic data will be linked to survey responses from routine DBI service data for those who consent; this will also help to reduce burden on participants.

At the end of DBI support, participating individuals will be emailed, text, handed in person or posted their second survey by the L2 DBI team.

- Surveys will take 15-20 minutes to complete and can be completed on paper or online and if requested translated versions will be supplied.
- An incentive of £10 will be distributed on completion of each the 4 surveys.
- For paper surveys, L2 staff will write the DIMES study unique identifier onto the paper survey before administering it.
- For online surveys, in their introductory email, individuals will be supplied with their unique DIMES study identifier to use to access their online survey.

Follow-up L2 DBI service users survey for individuals accessing DBI – at 3-4 months and 1 year following the start of the DBI intervention

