Using the contact details provided by participants in their consent form and/or their second survey, online or paper surveys will be sent by the ScotCen research team to all evaluation participants at 3-4 months and 1 year following their final DBI session to capture any on-going impact of DBI. In addition to repeating the scales collected in the initial surveys, the follow-up surveys seek to measure help-seeking behaviour improvement, other positive outcomes related to DBI presenting problems/life circumstances e.g. physical health, relationships, addictions, financial, and ask whether further support from DBI would be beneficial, what form this might take and why. Two brief reminders will be sent for each of the follow-up surveys (supporting documents 19 and 20).

A £10 thank you voucher will be provided to participants on completion of each of the four surveys above.

5.2.2 Linkage of individual level DBI L2 individual survey data with routine DBI data

Individual level data linkage between the DIMES participant survey dataset and DBI routine dataset will be undertaken for all evaluation participants who give their consent. This will enable the study team to link outcome data with service user characteristics and DBI intervention activity to facilitate analysis of service user sub-groups and intervention factors such as number of sessions, intervention length and onward referral.

Public Health Scotland (PHS) hold the DBI routine dataset. The linkage will be facilitated by ScotCen supported by [name] who is responsible for managing the DBI routine datasets at PHS. The linked dataset will be stored securely in the Safe Haven for the study team to access remotely. ScotCen would securely transfer the DIMES participant survey dataset to PHS via Secure File Transfer Protocol with the DIMES study unique identifier to enable linkage of the survey data to the DBI routine dataset (which also includes the DIMES study unique identifier).

We will also link the above combined dataset to the Unscheduled Care Datamart (UCD) to examine differences in unscheduled care use one year before and after DBI.

Permission to undertake this linkage will be sought from the Public Benefits and Privacy Panel.

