5.3 Data analysis

Survey data analysis will include descriptive statistics and crosstabulation analysis with logistic regression if appropriate. We will compare demographic, referral source and presenting problem characteristics of survey respondents and non-respondents to assess the representativeness of the survey sample and whether any weighting adjustments are required.

Qualitative survey data will be coded using a staged content approach. Qualitative interviews will be summarised, charted and coded using QSR NVivo 12 and analysed with reference to techniques of framework analysis. Focus groups will be analysed using a framework matrix to explore themes across the data₃₇. We will explore any differences or similarities in the views of the DBI and control qualitative participants to assess any perceived impact of the DBI intervention, while paying attention to other contextual influences.

The data linkage analysis will assess whether the difference in frequency of unscheduled care in the year post intervention differs between DBI participants and the comparator group by doubly robust estimation₃₄ adjusted for unscheduled care received in the preceding year. This analysis will include adjustment for potentially confounding sociodemographic variables. Secondary analyses and likely zero inflation will be assessed. A full Statistical Analysis Plan will be developed prior to the identification of the comparator group. For the health economic analysis, units of each item for all care pathways and for participant resource use will be collated and presented along with unit costs which will be derived from local sources as well as those which are publicly available₃₈.

A summative data synthesis will be undertaken to draw together the above through a process of triangulation to develop evidence-based insights and conclusions. Throughout the study, the study team and the SAG, will meet to share thematic and theoretical insights from data collection and analysis and develop interpretive connections and points of synthesis. Policy and practice recommendations will be made.

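### At the final-session survey the effect of L2 length cannot be separated from recovery time, and at every wave length follows need, so the word impact is not supported

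*Protocol*

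**What the plan says.** Among the research questions in section 4 is: "How does the length of the DBI L2 intervention impact on the above outcomes". The outcomes meant are those in the immediate, short and longer term.

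Section 1 (Background) gives a 14-day target but says it is set "to ensure the service is brief but intervention length is tailored to individual needs". It adds that 55% of people "complete DBI L2 by 14 days, 25% by 21 days and 20% within a month or more".

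Section 5.2.1 collects surveys 1 and 2 "at their first and final DBI L2 sessions for baseline and immediate outcome data (approximately two weeks apart"; Appendix 2 also puts the second survey at the final session. Section 5.2.2 links the surveys to routine data so that outcomes can be analysed by "intervention factors such as number of sessions, intervention length and onward referral".

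For the analysis, section 5.3 says: "Survey data analysis will include descriptive statistics and crosstabulation analysis with logistic regression if appropriate". It names no handling of need or elapsed time for the length question.

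The protocol is not consistent on timing. Section 4.2 defines the immediate outcome as 1 month, whereas section 5.2.1 and Appendix 2 use the final session. Appendix 2 has a column one month after the final session, but only screening and interviews fall there, not a survey. The sub-heading in 5.2.1 counts the later surveys from the start of DBI; the text under it and Appendix 2 count them from the final session.

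**The concern.** Two separate features affect the length question.

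First, survey 2 is triggered by the end of support. Someone supported for 14 days is measured about 14 days after baseline, and someone supported for a month about a month after baseline. If distress eases with time after a crisis, longer support can look better at survey 2 for that reason alone. The protocol itself expects such easing: the risk table in section 8.1 presumes that distress may have lessened a month after referral, and section 5.2.4 expects regression to the mean after the index event.

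Second, length is not assigned. Because it follows individual need, people with long and short stays may differ in prognosis before any effect of length, and this applies at all waves.

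A cross-tabulation of outcome by length could therefore show a difference in either direction when length does nothing. The findings are meant to feed DBI's continuous improvement programme (section 9.1.2), so a length table read causally could mislead its users.

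**Working it through.** **Base sample.** Section 7.2.1 expects 6000 referrals and cites 46% first-survey completion. 0.46 × 6000 = 2760, against the stated 2,700 (2.2% apart; 45% gives exactly 2700). Its later waves are 1350, 675 and 330. No sample size is stated for the length question.

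**Elapsed time at survey 2.** Time from baseline = length of support + any delay in returning the survey. Taking 14 days for the first band and 30 days as the shortest reading of a month or more, the ratio is 30/14 = 2.1. The two weeks of section 5.2.1 describes the 55% band, not the other 45%.

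**Numbers by length band.** Applying 55/25/20% to each wave (assuming respondents follow the bands for DBI users as a whole), with the detectable longest-versus-shortest difference = (1.96 + 0.84) × √(1/n₁ + 1/n₃) at 80% power and two-sided 5%:

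| Wave | ≤14 days | by 21 days | month or more | Detectable difference |
|---|---|---|---|---|
| Survey 2 (1350) | 743 | 338 | 270 | 0.20 SD |
| 3-4 months (675) | 371 | 169 | 135 | 0.28 SD |
| 1 year (330) | 182 | 82 | 66 | 0.40 SD |

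**Illustration with no true effect of length.** All inputs except the band shares are assumed: lengths of 14, 21 and 30 days; correlation of baseline severity with length 0, 0.2 or 0.4; baseline measure with reliability 0.8; outcome = 0.6 × severity − (1 − exp(−r × days/7)) + noise of SD 0.8, with r = 0.1 or 0.2 per week; N = 400,000.

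The elapsed-time part can be checked by hand. At the final session with r = 0.1: exp(−30 × 0.1/7) − exp(−14 × 0.1/7) = 0.651 − 0.819 = −0.17. With r = 0.2: 0.424 − 0.670 = −0.25.

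Longest minus shortest group, in baseline-severity SD (negative means longer looks better):

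| Outcome time | Unadjusted, correlation 0 | Unadjusted, correlation 0.2-0.4 | Adjusted for measured baseline, correlation 0.2-0.4 |
|---|---|---|---|
| Final session | −0.25 to −0.17 | +0.01 to +0.34 | −0.20 to −0.05 |
| 90 days after final session | −0.05 to −0.02 | +0.21 to +0.49 | +0.01 to +0.09 |
| 90 days after start | about 0 (+0.01) | +0.25 to +0.51 | +0.05 to +0.12 |

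Baseline adjustment does not remove the false benefit at the final session, because the elapsed-time part remains. At 90 days the elapsed-time part is small or absent, and what adjustment leaves is mainly residual confounding from imperfectly measured need. The slightly lower figures counted from the final session are not a reason to prefer that anchor: there, a small elapsed-time bias partly cancels the residual confounding.

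**The case against.** The strongest reply is that the protocol already collects what an acceptable analysis needs. Distress, suicidality, self-harm and entrapment are measured at the first session, length and service-user characteristics are linked, and the scales are repeated at 3-4 months and 1 year. This stands. A reader might infer that the length question cannot be answered at all; the documents do not support that, because an adjusted association at the later waves is feasible.

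Covariates and choice of model are commonly left to a statistical analysis plan, and section 5.3 mentions logistic regression, so an unadjusted cross-tabulation is not a commitment. This also stands, and the lack of a covariate list is not the point here. But the timing of survey 2 is fixed by data collection, and no analysis plan can undo it. The causal wording is the protocol's own; the question on unscheduled care in the same list is worded as an association.

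Third, need may not mean baseline severity: it could reflect practical problems or scheduling. This stands. A reader might infer that the two biases run in known, opposite directions, or take the simulated sizes as estimates. The documents give no basis for either.

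Fourth, survey 2 can be emailed or posted, so completion may lag the final session. That adds a delay to the elapsed time; it does not break its tie to length.

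Finally, a reader might infer that this analysis will set the 14-day target or decide on a Level 3. No section says so, and Level 3 is also addressed through follow-up survey items, interviews and staff focus groups.

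**Conclusion.** The point holds in two parts. For the immediate outcome only, length and elapsed recovery time are essentially one quantity at survey 2, across a spread from 14 days or less (55%) to a month or more (20%), and adjustment cannot separate them. At every wave, length follows individual need, so a comparison by length is open to confounding and does not support a causal reading.

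The first part rests on the protocol's own schedule and length bands. That elapsed time matters for outcome rests on distress easing over time, which the protocol itself presumes. The size and direction of the net bias are unknown; the simulated figures show a pattern under assumed inputs and nothing more. It should be corrected because wording and analysis choices using data already planned would deal with most of it.

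**What to change.** - **Section 4:** ask about association, for example: *How is L2 duration associated with these outcomes?*
- **Section 5.3:** state that survey 2 differences by length will not be interpreted as an effect of length. Base the length analysis on the 3-4 month and 1-year surveys, using a regression adjusted for first-survey distress, suicidality/self-harm and entrapment, and for presenting problem and referral source. Report it as an exploratory association and acknowledge residual confounding by need.
- **Sections 4.2, 5.2.1 and Appendix 2:** reconcile the timing of the immediate outcome (1 month or final session) and the anchor for the later surveys (start of DBI or final session).
- **Elapsed time:** if follow-up runs from the final session, days since the first session equals length plus the follow-up interval, so using it as a covariate largely re-enters length. Compare lengths at a common time from the start of DBI where possible; otherwise state that some overlap with elapsed time remains.

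The variables are already in the surveys or the linked data, so the main change is to wording. The price is fewer respondents: about 675 and 330 instead of 1350, with about 135 and 66 long-stay respondents if the bands apply. The detectable longest-versus-shortest difference rises from about 0.20 SD to 0.28 and 0.40 SD, and the claim becomes weaker and non-causal.
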